7.2.3.5 Electrocardiography (ECG)

A 12 lead ECG should be collected after the participant has been in a supine position for at least 5 minutes.

If abnormal results are observed, the investigator will assess clinical significance and determine whether the results should be recorded as an AE.

The timepoints for ECG collection is noted in [Table 1](#).

7.2.3.6 Cardiodynamic 12-Lead Electrocardiography (ECG) Monitoring

Select sites will participate in a sub study using a continuous 12 lead ECG recorder. For more details refer to Appendix 5.

7.2.3.7 Clinical Laboratory Evaluations

All clinical laboratory assays will be performed according to the institution's laboratory normal procedures. If there are laboratory collections that are not done by the institution's laboratory, the institution should follow their standard procedures for sending samples to their reference laboratories for analysis (e.g., AEDs). The collection timepoints are detailed in [Table 1](#). Reference ranges are to be supplied by the laboratory and will be used to assess the clinical laboratory data for clinical significance and out of range pathologic changes. The investigator should assess out of range clinical laboratory values, indicating if the values are clinically significant or not clinically significant. Abnormal clinical laboratory values that are unexpected or not explained by the participant's clinical condition may, at the discretion of the investigator or Sponsor, be repeated as soon as possible until confirmed, explained, or resolved.

Urine Chemistry

Urine samples for N-acetyl- β -D-glucosaminidase (NAG), β 2-microglobulin, and creatinine will be collected at the times specified in Table 1. Urine samples will be stored frozen. Details regarding sample collection, processing, storage, and shipment to the bioanalytical vendor are described in the Biospecimen Manual.

Drugs of Abuse Testing

A urine or serum sample for drugs of abuse testing should be collected per the institution standard of care and prior to IP initiation. A urine or serum sample for alcohol testing should be collected if medically indicated. If medically indicated, the investigator may expand testing for additional drugs of abuse above the institution's standard of care. If unable to collect predose, collect as soon as possible following IP initiation. However, if a participant tests positive, it will be at the investigator's discretion to weigh the risks versus benefits for enrollment or continued participation. If the investigator decides to discontinue the IP, refer to [Section 4.5](#).

Pregnancy Test

As described in [Table 1](#) and [Section 4.4](#), a urine or serum pregnancy test should be collected for all females of childbearing potential prior to IP initiation, and if pregnancy is suspected. If unable to collect predose, collect as soon as possible following IP initiation. Enrollment is not contingent upon results. However, if a participant has a positive test result, it will be at the investigator's discretion to weigh the risks versus benefits for continued participation. If the investigator decides to discontinue the IP, please refer to [Section 4.5](#). If the institution requires the pregnancy test results be obtained prior to IP initiation, the institution guidelines will be followed.

Blood Gas

All blood gas samples arterial or venous, if collected, will be at the investigator's discretion to manage care. If collected from the time of SE diagnosis through the end of the first 24 hours of the follow-up period, the eCRF should be completed. If samples are not collected, a sample will not be required.

If a decision is made to intubate the participant between IP initiation through the end of the first 24 hours of the follow-up period, a blood sample should be collected. The sample should be collected immediately prior to or as close as possible to the time of intubation.

The clinical laboratory tests performed as part of the protocol are listed in Table 6.

Table 6. Clinical Laboratory Tests

Hematology	Coagulation	Biochemistry	Urinalysis
Hemoglobin (Hb)	Fibrinogen	Sodium	pH
Hematocrit (Hct)	Activated partial thromboplastin time (aPTT)	Potassium	Protein
Red blood cell count (RBC)	Prothrombin time (PT)	Calcium	Blood
White blood cell count; total and differential (WBC)	International normalized ratio (INR)	Glucose	Ketones
Mean corpuscular hemoglobin (MCH)		Total protein	Glucose
Mean corpuscular hemoglobin concentration (MCHC)		Albumin	Bilirubin
Mean corpuscular volume (MCV)		Creatinine	Specific gravity
Platelet count		Blood urea nitrogen (BUN)	If any abnormal value is observed on the urine dipstick test, the sample should be further analyzed with urine microscopy:
WBC Differential		Total Bilirubin	WBC
% Basophils		Alkaline phosphatase (ALP)	RBC
% Eosinophils		Aspartate transaminase (AST)	Cellular casts
% Lymphocytes		Alanine transaminase (ALT)	Granular casts
% Monocytes		Total cholesterol ¹	Hyaline casts
% Neutrophils		Estimated Glomerular Filtration Rate (eGFR), if available	
Basophil count		Creatinine Clearance calculation, if available	
Eosinophil count			Urine or Serum Drugs of Abuse Testing
Lymphocyte count		Urine Chemistry	(per institution standard of care)
Monocyte count		N-acetyl-β-D-glucosaminidase [NAG]	Phencyclidine
Neutrophil count		B2-microglobulin	Opioids ²
		Creatinine	Cannabinoids ³
			Methamphetamine/Amphetamine
		Antiepileptic drug levels (AEDs; per institution standard of care)	Cocaine
		fosphenytoin/ phenytoin, valproic acid, levetiracetam, lacosamide, phenobarbital or brivaracetam	Barbiturates
			Benzodiazepines
			Alcohol, if medically indicated
			Urine or Serum Pregnancy

1. Total cholesterol level, if collected per standard of care, should be collected predose (screening).
2. May be limited to drug class or list specific drug such as oxycodone, methadone, heroin.
3. May be limited to drug class or list specific substance such as THC.

7.2.4 Others

7.2.4.1 Clinical Pharmacology Blood Sample Collection and Handling Procedures

Blood samples for pharmacokinetic analysis (PK) will be collected at the times specified in Table 2. The Sponsor's expectation is that the investigator will ensure that every effort is made to collect all PK blood samples at the precise protocol scheduled time. Pharmacokinetic blood collection must not deviate from the nominal collection time set forth in the protocol by more than \pm 5 minutes for samples drawn within 6 hours following IP initiation or by more than \pm 2 hours for samples drawn beyond 36 hours following IP initiation. Samples drawn outside these parameters will be considered a protocol deviation.

Venous blood samples (2 mL) will be drawn from indwelling catheters or by direct venipuncture into K₂EDTA Vacutainer® tubes (lavender top), capped, mixed by inversion ($\times 10$), and chilled immediately on crushed ice. If using indwelling catheters, they should be kept patent with isotonic saline and the saline should be withdrawn (1 mL) and discarded before the blood sample is taken. Use of topical anesthesia to reduce the pain of an indwelling catheter is permitted and, if used, should be documented as a concomitant medication. If venous blood sample collection is not possible an arterial sample may be collected. The type of sample will be recorded in the source documents and eCRF.

Pharmacokinetic samples should be collected from the contralateral peripheral access or the arterial line and avoid collecting samples downstream of the IP infusion. The location of IP access and location of PK sample collection should be documented in the participant's source. If the PK sample cannot be collected due to poor venous access and the IP infusion site is the only viable option, the sample should not be collected and the reason for non-collection documented in the participant's source.

Details regarding sample collection, processing, storage, and shipment to the bioanalytical vendor are described in the Biospecimen Manual. The freezer temperature where these samples are stored must be controlled, monitored, and recorded during the storage period until the samples are shipped on dry ice to the bioanalytical vendor for analysis. The Sponsor must be notified of any temperature excursions.

7.2.4.2 Shipment of Plasma Pharmacokinetic Samples

Unless agreed upon by the Sponsor, within approximately 1 week after participants complete the first 24 hours of the follow-up period, the site will ship the primary plasma samples to the bioanalytical vendor. Upon notification of receipt of the primary samples by the bioanalytical vendor, the backup samples will be shipped to the bioanalytical laboratory. Refer to the Biospecimen Manual for details regarding sample shipping.

7.2.4.3 Plasma Drug Assay Methodology

Plasma concentrations will be measured using the most current validated liquid chromatography with tandem mass spectrometry (LC/MS/MS) method. Other metabolites may be monitored or quantitated as appropriate. Raw data will be stored in the archive of the designated bioanalytical laboratory.

Table 7. Volume of Blood to Be Drawn from Each Participant

Assessment		Sample Volume (mL) ^a	Number of Required Collection Timepoint Samples	Number of Variable Collection Timepoint Samples	Total Volume (mL)
Safety ^b	Biochemistry (with indwelling catheter)	8.5	5	3	42.5 to 68
	Hematology	4.0	5	3	20 to 32
	Coagulation	5.1	3	1	15.3 to 20.4
Pharmacokinetic samples (with indwelling catheter) ^c		3.0	8	0	24
Blood gas (for intubation only) ^b		1.0	0	1	1
Total mL					140.3 to 190.4

- a. If a catheter is used, the first milliliter (mL) collected is to be discarded, then the required volume is collected into the appropriate tube for the assessment. This additional 1 mL has been added to the biochemistry and pharmacokinetic collections noted in the table. This assumes the hematology, coagulation, and AED samples will be collected at the same times as the biochemistry samples. The collection volume for coagulation testing at sites ranged from 2.7mL to 7.5.0mL, as such the median volume of 5.1mL was used for the table calculation.
- b. See Table 1 for sample collection timepoints. There are required collection timepoints for all participants and variable collection timepoints that only apply in specific situations. The two different types have been separated in the table to show the maximum and minimum number of sample collections for a participant.
- c. Blood samples for pharmacokinetic analysis will be collected as noted in [Table 2](#).
- d. Venous or arterial samples are acceptable.

Table 8. Volume of Blood to Be Drawn from Each Participant (Pediatric Institution Sample Volumes)

Assessment		Sample Volume (mL) ^a	Number of Required Collection Timepoint Samples	Number of Variable Collection Timepoint Samples	Total Volume (mL)
Safety ^b	Biochemistry (with indwelling catheter)	2.0	5	3	10 to 16
	Hematology	1.0	5	3	5 to 8
	Coagulation	1.0	3	1	3 to 4
Pharmacokinetic samples (with indwelling catheter) ^c		3.0	8	0	24
Blood gas (for intubation only) ^b		1.0	0	1	1
Total mL					36 to 40

- a. If a catheter is used, the first milliliter (mL) collected is to be discarded, then the required volume is collected into the appropriate tube for the assessment. This additional 1 mL has been added to the biochemistry and pharmacokinetic collections noted in the table. This assumes the hematology, coagulation, and AED samples will be collected at the same times as the biochemistry samples.
- b. See Table 1 for sample collection timepoints. There are required collection timepoints for all participants and variable collection timepoints that only apply in specific situations. The two different types have been separated in the table to show the maximum and minimum number of sample collections for a participant.

c. Blood samples for pharmacokinetic analysis will be collected as noted in [Table 2](#). Venous or arterial samples are acceptable.

During the study, it is expected that some sites (e.g., pediatric institutions) will collect smaller volumes of blood from participants per local laboratory standards. The ranges in [Table 7](#) and [Table 8](#) reflect the possible range for adult and child versus a pediatric only institution. The total blood volume drawn from pediatric participants for all safety and pharmacokinetic sampling will be approximately 36 mL and will not exceed 40 mL. The total blood drawn from adult participants will be approximately 140.3 mL and will not exceed 190.4 mL.

As noted in [Table 1](#), several of the collection points are considered optional; however, to provide the most conservative estimate of the blood volume drawn, these optional collections have been included in [Table 7](#) and [Table 8](#).

Note: The amount of blood to be drawn for each assessment is an estimate. The amount of blood to be drawn may vary according to the instructions provided by the manufacturer or laboratory for an individual assessment. When more than one blood assessment is to be done at a single timepoint/period, if they require the same type of collection tube, the assessments may be combined.

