10. Pregnancy test for females of childbearing potential, should be collected predose (screening). Samples can be urine or serum. If unable to collect predose, collect as soon as possible following IP initiation. Enrollment is not contingent upon results. However, if a participant has a positive test result, it will be at the investigator's discretion to weigh the risks versus benefits for enrollment or continued participation. If the institution requires the pregnancy test results to be obtained prior to IP initiation, the institution's guidelines will be followed.
11. Electroencephalogram is required for confirmation of CSE and NCSE diagnosis. Ideally, continuous EEG monitoring should start at least 60 minutes before IP initiation and continue through the end of the first 24 hours of the follow-up period.

Sites will be offered the use of a rapid EEG device to assist with screening of participants with NCSE. It is preferred that a conventional EEG is used for the purposes of confirming inclusion criterion #3 and EEG monitoring during IP administration. In situations when a conventional EEG is not immediately available, the rapid EEG may be used to confirm inclusion criterion #3. Since the rapid EEG has a limited battery life, it should be switched to a conventional EEG within several hours but not earlier than 90 minutes after IP initiation to allow uninterrupted collection of EEG for the 30-minute SE cessation co-primary endpoint. It will be at the investigator's discretion if the use of the rapid EEG will benefit their site. The device should be used according to institution standard practices.

12. Blood sampling (venous or arterial) for pharmacokinetic (PK) analysis of ganaxolone and Captisol® will be collected at the following times:

Required collections:

- a. After the start of the IP infusion: 60 minutes (+/- 5 min), then 2, 6 (+/- 5 min), 10, 24 and 36 hours (+/- 2 hour) following IP initiation,
- b. At the time of IP discontinuation (+/- 1 hour), either at the end of the taper or if the IP administration is stopped without a taper (e.g., when the participant progresses to IV anesthesia for seizure/SE treatment), and
- c. 24 hours (+/- 1 hour) following IP discontinuation.

Variable PK collection times based on participant response:

Between IP initiation and at the end of the first 24 hours of the follow-up period, where possible, collect a PK sample:

- d. At the time of an SAE (related or not related)

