Participants who terminate early from the study, e.g., due to withdrawal of consent, should have early termination procedures completed when early termination is being considered, wherever possible.

Participants who discontinue IP with or without a taper (e.g., were administered IP for less than 2 hours, progress to anesthesia for seizure suppression or discontinue IP due to safety or any other reason except due to withdrawal of consent) will continue in the study. The follow-up period assessments/procedures will be collected every 24 hours through 120 hours (or until hospital discharge) and at the time of hospital discharge, followed by weekly follow-up visits/contacts at Week 1, 2, 3, and 4.

All participants who discontinue IP, except those who are terminated early from the study, will have the follow-up period assessments/procedures, and the follow-up visits/contacts at Week 1, 2, 3, and 4. Weeks 1, 2, 3 and 4 visits can be conducted as an inpatient visit, if the participant is still in the hospital or as a telephone contact, if the participant has been discharged. Attempts should be made to have discharged participants return for one of these visits to be in person.

During these visits/contacts, the site will follow-up on all SAEs and AEs, and medications administered. Each participant will be followed for approximately 4 weeks.

During the study, it is expected that the total blood volume drawn from pediatric participants for all safety and pharmacokinetic sampling will be approximately 36 mL and will not exceed 40 mL of blood. The total blood drawn from adult participants will be approximately 140.3 mL and will not exceed 190.4 mL.

Inclusion and Exclusion Criteria:

Inclusion Criteria:

1. Participant, participant's parent, guardian, or LAR must provide signed informed consent/assent, and once capable (per institutional guidelines), there must be documentation of consent/assent by the participant demonstrating they are willing and aware of the investigational nature of the study and related procedures. Where allowed by law, if the patient lacks the capacity to make informed decisions regarding his/her medical treatment options, the treating clinician may follow their deferred consenting practices. The clinician will make the final decision based on the best interests of the patient.
2. Male or females 12 years of age and older at the time of the first dose of IP.
3. SE meeting the following criteria:

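### The blood-volume totals in Protocol Tables 7 and 8 are not the sums of their rows, and the pediatric rows exceed the stated 40 mL limit

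*Protocol*

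**What the plan says.** Protocol section 7.2.4.3 gives two blood-volume tables. Table 7 covers the general case and Table 8 covers pediatric-institution sample volumes. Each row lists a volume per sample, a number of required samples, a number of variable samples and a row total. The last line of each table prints an overall total: 140.3 to 190.4 mL in Table 7 and 36 to 40 mL in Table 8.

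The text below Table 8 turns both totals into an expected volume and a ceiling. For pediatric participants the volume "for all safety and pharmacokinetic sampling will be approximately 36 mL and will not exceed 40 mL". For adults: "The total blood drawn from adult participants will be approximately 140.3 mL and will not exceed 190.4 mL". The synopsis, under study follow-up and discontinuation, repeats the pediatric statement ("will be approximately 36 mL and will not exceed 40 mL of blood") and the adult figures.

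Two notes say what the rows contain. Footnote a states "If a catheter is used, the first milliliter (mL) collected is to be discarded" and adds that this extra 1 mL is already inside the biochemistry and pharmacokinetic (PK) volumes. The text below Table 8 says of the optional collections: "to provide the most conservative estimate of the blood volume drawn, these optional collections have been included in" the two tables. It also calls the volumes estimates and allows assessments that share a tube type to be combined.

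**The concern.** A printed total should equal the sum of its rows, and neither does. The errors run in opposite directions, so one common omission or rounding rule cannot explain both. Table 7 prints more than its rows add to. Table 8 prints less, and its total is the basis for a statement worded as a limit.

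The trial enrolls from age 12. An ethics committee or site would read the pediatric sentence as a participant-protection commitment. If the protocol's own schedule draws more than the limit, the protocol contradicts itself on what minors and their families were told. The adult discrepancy overstates the volume, so its ceiling is not breached.

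**Working it through.** **Inputs.** All come from Tables 7 and 8 as printed. The minimum is the sum of (volume × required samples). The maximum is the sum of (volume × (required + variable samples)).

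| Row | Samples (required + variable) | Table 7: volume → row total (mL) | Table 8: volume → row total (mL) |
|---|---|---|---|
| Biochemistry | 5 + 3 | 8.5 → 42.5 to 68 | 2.0 → 10 to 16 |
| Hematology | 5 + 3 | 4.0 → 20 to 32 | 1.0 → 5 to 8 |
| Coagulation | 3 + 1 | 5.1 → 15.3 to 20.4 | 1.0 → 3 to 4 |
| PK | 8 + 0 | 3.0 → 24 | 3.0 → 24 |
| Blood gas | 0 + 1 | 1.0 → 0 to 1 | 1.0 → 0 to 1 |

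**Row products.** The biochemistry, hematology, coagulation and PK totals all match the printed ones (for example 8.5 × 5 = 42.5 and 8.5 × 8 = 68). The blood gas row prints 1 mL; with no required sample it adds 0 to the minimum and 1 to the maximum.

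**Totals, rows as printed.**

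- Table 8 minimum: 10 + 5 + 3 + 24 = **42 mL** (printed 36). Counting the blood gas would give 43.
- Table 8 maximum: 16 + 8 + 4 + 24 + 1 = **53 mL** (printed 40).
- Table 7 minimum: 42.5 + 20 + 15.3 + 24 = **101.8 mL** (printed 140.3; difference 38.5).
- Table 7 maximum: 68 + 32 + 20.4 + 24 + 1 = **145.4 mL** (printed 190.4; difference 45.0).

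**Can another reading of the rows recover the printed totals?** The distance from minimum to maximum depends only on the variable draws. In Table 8 they add 6 + 3 + 1 + 1 = 11 mL, or 8 mL with no discard; the printed distance is 4 mL. In Table 7 they add 25.5 + 12 + 5.1 + 1 = 43.6 mL; the printed distance is 50.1 mL. Dropping rows, adding or removing discards, using the ends of the stated coagulation range (2.7 or 7.5 mL), or adding one PK draw does not give both ends of either total. A row lost from the table could not explain Table 8, because its printed total is below the visible sum.

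**Alternative readings of Table 8.**

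- *No catheter discard.* Section 7.2.4.1 says "Venous blood samples (2 mL) will be drawn from indwelling catheters or by direct venipuncture", so a discard is not inevitable. With biochemistry at 1 mL and PK at 2 mL, the minimum is 5 + 5 + 3 + 16 = 29 mL and the maximum is 8 + 8 + 4 + 16 + 1 = 37 mL.
- *No weekly draw.* After discharge, the weekly laboratory draw is made only when possible. If it is the fifth required draw (the tables do not label their timepoints, so this is an assumption), the minimum is 42 − (2 + 1) = 39 mL.

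**Omitted sample.** The synopsis (Safety and Assessments, item 12) and Table 2 footnote b call for a PK sample at a serious adverse event where possible, yet both tables count 0 variable PK samples. One such sample gives 53 + 3 = **56 mL** in Table 8, or 37 + 2 = 39 mL without discards. In Table 7 it gives 145.4 + 3 = **148.4 mL**, which is 42.0 mL below the printed 190.4.

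**The case against.** The strongest objection concerns Table 7. Its footnote a still assumes that antiepileptic drug (AED) samples are drawn with biochemistry, but the table has no AED row. A row of 7.5 mL with 5 required and 1 variable sample, with blood gas counted as 1 mL at both ends, would reproduce both printed totals: 101.8 + 1 + 37.5 = 140.3 and 145.4 + 45 = 190.4. The amendment history, which records removal of an AED row, fits that explanation. So the adult total is probably left over from a deleted row. This explains the error but does not remove it: AED levels are now taken only if collected as part of standard care, and the total still does not follow from the table. It does leave open whether such draws should be counted, and the sponsor should say so.

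Second, Table 8 charges a discard to both biochemistry and PK at IP discontinuation and again 24 hours later. If one catheter draw serves both purposes, two discards disappear and the required draws become 42 − 2 = 40 mL, which does not exceed the limit. That is fair, but the maximum is then still 53 − 2 = 51 mL.

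Third, 53 and 56 mL are table ceilings. An early-termination draw would usually replace a later required one; removing one 3 mL draw from the maximum gives 53 − 3 = 50 mL, still over 40. A sample at a serious adverse event is taken only where possible.

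Fourth, the volumes are described as estimates and tubes may be combined. That can change what is actually drawn, but it does not make a total equal its rows, and the pediatric sentence is worded as a ceiling.

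Finally, no analysis is affected, and section 3.1.1 says randomization stopped at 100. This limits the consequence of the error but leaves the contradiction in place.

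**Conclusion.** The concern holds. Neither printed total follows from its own table.

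- **Pediatric, rows as printed:** required draws are 42 mL, which is 6 mL (17%) above the stated 36 mL and 2 mL (5%) above the 40 mL limit. The maximum is 53 mL, 13 mL (33%) over the limit, or 56 mL with one event-triggered PK sample, 16 mL (40%) over.
- **Adult:** the printed total is 38.5 mL too high at the minimum and 45.0 mL too high at the maximum. This is an overstatement, not a breach.

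The pediatric breach is shown for participants sampled as Table 8 is written, with a catheter discard at each biochemistry and PK draw. It is not shown for every pediatric participant: with no discards the limit is met. On the shared-discard and no-weekly-draw readings the required draws do not exceed it. None of these readings reproduces 36 to 40 mL.

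With randomization stopped, what remains is the accuracy of the protocol and of what ethics committees were told. No endpoint, efficacy test or safety analysis changes. The documents give no blood-volume safety threshold, so no participant harm is claimed.

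**What to change.** 1. Recompute the totals in Tables 7 and 8 from the rows, with the PK sample at a serious adverse event entered in the variable column. On the rows as printed, with one such sample, this gives 42 to 56 mL (pediatric) and 101.8 to 148.4 mL (adult).
2. State whether a catheter discard is assumed at every draw, including when biochemistry and PK are taken together.
3. State whether AED levels drawn under standard care are counted. Then either restore a row or remove the mention from footnote a of both tables.
4. Carry the same figures into the text below Table 8 and into the synopsis.
5. Reconcile the pediatric ceiling with the scheduled draws and volumes. The documents do not show whether the limit or the rows should change, so that is for the sponsor to settle.

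The cost is a text and table correction with notice to ethics committees. The sponsor may have to state a less favorable pediatric figure or explain the discard assumption. No analysis changes.
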